We will randomly select a subset of 30 samples from patients with similar overall 16S abundance, but 15 samples will have abundant *LBP* and 15 additional samples will have undetectable *LBP*. We will utilize the Illumina HiSeq2000 platform, aiming for a mean of 10 gigabases of 101 bp paired-end reads per sample. For comparative quantification of gene content at the individual gene level and the level of KEGG metabolic pathways, we will utilize linear discriminate analysis (LDA) effect size (LEfSe) analysis⁸⁹ for biomarker discovery. In addition to comparing samples with abundant and reduced *LBP* levels, we will also examine samples from patients who did or did not develop aGvHD. With this approach, we hope to identify novel bacterial genes and gene pathways, some of which may be *LBP*-derived, that are associated with modulation of aGvHD and may play a role in aggravating or attenuating inflammation. As all correlative assays will be performed on the backbone of a COG clinical trial, we anticipate high quality and very complete assessment laboratory findings.

7.3.3.2 **Evaluating the effects of LBP introduction on intestinal flora function via functional metabolite profiling**

While whole shotgun metagenomic sequencing provides information regarding the functional potential of the intestinal flora, a complementary approach is to assay directly for demonstration of substrate utilization and metabolite production. By determining bacterial metabolite abundances, one can confirm that increased abundance of individual genes and genes of metabolic pathways are associated with a corresponding increase in enzymatic activity. This method can also identify novel bacterial metabolites that are biologically active. One example of a group of metabolites that have garnered interest recently is short-chain fatty acids (SCFA), which are produced by many bacteria as a byproduct of carbohydrate fermentation. SCFA have been found to be important modulators of the immune system. In germ-free mice and vancomycin-

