treated conventional mice, administration of SCFA (acetate, propionate, or butyrate) restored normal numbers of Tregs in the large intestine.⁸⁴ GPR43 (a SCFA receptor) has been identified as necessary for mediating the anti-inflammatory effects of commensal bacteria⁹⁶ and is required for restoration of large intestinal Tregs by SCFA.⁸⁴ We will quantitatively profile levels of enzymatic substrates and metabolites via UHPLC-MS services coupled with an extensive library with >2800 authenticated compounds provided by Metabolon (Durham, NC). We will profile aliquots of the same stool samples selected for the whole shotgun metagenomic sequencing approach detailed above as well as paired serum samples collected at the same time as the stool samples. A recent study linking intestinal flora with severity of an autism-like syndrome in mouse models similarly utilized Metabolon's services to identify a serum metabolite that induced anxiety-like behavior in these mice. Interestingly, the levels of this metabolite were modulated by intestinal flora composition.⁹⁷ Using this approach, we will **identify novel bacterial metabolites, some of which may be LBP-derived, that are associated with modulation of aGvHD** and may play a role in either aggravating or attenuating inflammation.

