Exploratory Aims 3 and 4: These aims will examine the effects of *LBP* introduction on the intestinal flora of pediatric alloHCT recipients. The association between *LBP* administration and bacterial genes and pathways, and bacterial metabolites will be evaluated with Pearson's correlation coefficient with possible transformation to approximate normality. In addition to confirming the significance, a 95% confidence interval will be estimated for each marker. The total length of the interval depends on the observed correlation; the length will be 0.53 if the correlation is 0.40 and 0.24 if the correlation is 0.8. In addition to correlation, bivariate scatterplots will be used to display the association between *LBP* administration and each marker. Finally, we will perform a descriptive analysis examining the association between GvHD outcomes and bacterial genes, pathways, and metabolites using Cox regression. Additional regression models will adjust for other known GvHD risk factors.

Exploratory Aim 5: This aim will examine the effects of *LBP* on pro-inflammatory cytokines in alloHCT recipients. We hypothesize that *LBP*-associated maintenance or restoration in the microbiota will attenuate serum levels of pro-inflammatory cytokines in the early post-transplant period. We will use the same analytic approach as described for exploratory Aim 2 above.

Exploratory Aim 6: This aim will examine the effects of LBP on the incidence (yes/no) of *Clostridium difficile*-associated diarrhea in alternative donor HCT patients. Patients who have at least one incidence (positive) of *C. diff* during any reporting period is considered evaluable for this aim. We will compare proportion of *C. diff* during the study period between arms via the chi-square test.

Exploratory Aim 7: This aim will examine whether LBP administration reduces hospital days within the first 120 days post hematopoietic cell transplant. Total hospital days over the study period is calculated as the duration between the date of admission for conditional therapy and the date of discharge (or the study end date). Hospital days will be compared between arms by t-test (or Wilcoxon rank-sum test if assumptions for t-test are not met).

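### Exploratory Aims 3 and 4 declare significance marker by marker across genes, pathways and metabolites, with no false-discovery control

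*Combined protocol and SAP*

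**What the plan says.** Section 9.3 (Exploratory Aims 3 and 4) states that the relation of LBP administration to "bacterial genes and pathways, and bacterial metabolites will be evaluated with Pearson's correlation coefficient with possible transformation to approximate normality". Every marker gets a significance statement and an interval: "In addition to confirming the significance, a 95% confidence interval will be estimated for each marker". On precision, it says that "the length will be 0.53 if the correlation is 0.40 and 0.24 if the correlation is 0.8", without giving the sample size behind those lengths. For the clinical outcome, "we will perform a descriptive analysis examining the association between GvHD outcomes and bacterial genes, pathways, and metabolites using Cox regression".

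Section 7.3.3 describes the material. For shotgun sequencing, "We will randomly select a subset of 30 samples from patients with similar overall 16S abundance", made up of 15 with abundant and 15 with undetectable LBP. Genes and KEGG pathways are also compared by LEfSe, for which no significance level, effect-size cut-off or multiplicity setting is given. A second grouping is planned: "we will also examine samples from patients who did or did not develop aGvHD". Metabolites are profiled in the same stool samples "as well as paired serum samples collected at the same time as the stool samples", on a platform "coupled with an extensive library with >2800 authenticated compounds provided by Metabolon".

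The plan does adjust for multiplicity elsewhere. Aim 2 applies Bonferroni to four citrulline contrasts (section 9.3, with the resulting alpha of 0.0125 in section 9.4), and Aim 5 adopts the Aim 2 approach for cytokines. Nothing comparable is written for Aims 3 and 4.

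**The concern.** A significance rule applied separately to hundreds or thousands of markers produces a predictable number of false declarations even when no marker is related to LBP. The plan recognises the problem for four citrulline contrasts but is silent for by far its largest family of tests. Section 7.3.3 says these aims are meant to identify new bacterial genes, pathways and metabolites linked to modulation of aGvHD. Without an error-rate rule, the published list would mix real and chance associations in unknown proportion, and later laboratory or clinical work could be built on the chance ones. What is at stake is the credibility of the discovery output, not the trial's efficacy conclusion.

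**Working it through.** **Inputs**
- Two-sided α = 0.05 per marker. This is an assumption read from the 95% interval in section 9.3; no level is stated for these aims.
- n = 30 samples, 15 versus 15 (section 7.3.3.1).
- Two matrices, stool and serum (section 7.3.3.2).
- More than 2,800 compounds is the size of the vendor library (section 7.3.3.2). The number to be analysed is not stated, so 500, 1,000 and 1,500 are taken as an assumed range below it.

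**1. The plan's own figure.** The length of a Fisher-z 95% interval is tanh(atanh r + 1.96/√(n−3)) − tanh(atanh r − 1.96/√(n−3)).
- n = 30: 0.62 at r = 0.40 and 0.28 at r = 0.8.
- n = 40: 0.53 and 0.24.

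The stated lengths fit 40 observations, not 30, and no subset of 40 samples is described. Section 9.3 also relates markers to LBP administration, whereas section 7.3.3.1 groups samples by LBP abundance. The two sections need to be reconciled. Neither point changes the count below, which depends only on the number of null markers and α.

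**2. Expected false declarations.** E = α × (number of null markers), per matrix, if no compound is related to LBP:
- 500 compounds: 0.05 × 500 = 25
- 1,000 compounds: 0.05 × 1,000 = 50
- 1,500 compounds: 0.05 × 1,500 = 75
- 2,800 compounds: 0.05 × 2,800 = 140

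At α = 0.01 (also an assumption), 2,800 compounds give 28. The chance of at least one false declaration among 300 independent tests at 0.05 is 1 − 0.95^300, which is above 0.999999.

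**3. Check by simulation.** This used 400 null data sets, Pearson correlation with a 15-versus-15 grouping, and 2,800 markers.
- Independent markers: mean 141 flagged, 95% range 119 to 163.
- Blocks of 100 markers with correlation 0.5: mean 139, range 66 to 234.

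Correlation between markers leaves the average unchanged but makes the count much less predictable.

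**4. The same data with Benjamini-Hochberg at 5%.** Mean false discoveries per run fall to 0.06 (independent) and 0.19 (blocks), and any false discovery occurs in about 5 to 6% of runs. At the 10% level proposed below, the chance of any false discovery under a complete null with independent markers would be about 10%.

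**5. Why not Bonferroni.** Over 2,800 tests the per-test level is 0.05/2,800 = 0.000018. At n = 30 the correlation needed rises from 0.36 (unadjusted) to 0.70, which is severe for discovery work.

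**6. Selected groups.** If marker and LBP were jointly normal with a true correlation of 0.30, the expected two-group coefficient would be 0.44 from the outer 15% tails, 0.32 from outer thirds and 0.24 from a split into halves. The plan does not say what fraction of samples counts as abundant or undetectable.

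**The case against.** The strongest reply is that these are exploratory aims, introduced in section 7.3.3 as discovery work, and that they touch neither the primary test nor the decision between stages. That stands, and it limits the reach of the point. It does not remove the point: section 9.3 asks for significance for each marker, and a false-discovery rate is the usual tool for exploratory work of this kind.

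A reader might also infer several stronger things that the documents do not support.
- **That more than 2,800 metabolites will be tested, giving 140 false hits.** The figure describes the library, not what will be detected or analysed, and α is inferred. The 140 is therefore an upper illustration.
- **That the same count recurs for aGvHD.** Section 9.3 uses Cox regression there, labels it descriptive, and its null is no association between marker and GvHD, not an inactive LBP.
- **That Pearson testing is the only method, or citrulline the only family corrected.** Genes and pathways also get LEfSe, and Aim 5 inherits the Bonferroni step.
- **That choosing abundant and undetectable samples necessarily inflates the correlations.** Step 6 shows that size and even direction depend on tail fractions the plan does not give. The calculation also treats LBP administration and abundance as one variable. What remains is that a coefficient from a selected subset need not estimate the trial-population value.
- **That the list would be mostly chance.** This depends on how many associations are real. As an assumed illustration, take 1,000 compounds, true r = 0.45 and n = 30. Power is about Φ(√27 × atanh 0.45 − 1.96) = Φ(0.56) ≈ 0.71. If 5% are real, about 36 true hits stand against 950 × 0.05 ≈ 48 false ones. If 20% are real, about 142 stand against 800 × 0.05 = 40.

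Finally, with a two-level LBP variable, Pearson's test on transformed data gives the same p-value as a pooled two-group t-test. Changing the effect measure therefore improves interpretation, not error control.

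**Conclusion.** The point holds as a gap in error control for an exploratory analysis, and it should be corrected before the omics data are analysed. Followed as written, the plan would declare about 5% of null markers significant: about 25 to 75 metabolites per matrix for 500 to 1,500 compounds analysed, and up to about 140 if the whole library were tested. These counts assume a two-sided 5% level and no true LBP associations among the compounds. They scale in proportion to the number of null markers. Genes and pathways add to them by an amount that cannot be worked out, because their number is not stated. The effect is on which markers are reported as discoveries. The primary comparison, its power and its type I error are unaffected.

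**What to change.** In section 9.3, for Aims 3 and 4:
1. State the marker set to be analysed for each platform and matrix, including any detection filter, and the number of samples. Reconcile the interval lengths with the 30 samples, and LBP administration with LBP abundance.
2. Apply Benjamini-Hochberg control at a stated level, for example 10%, within each platform, matrix and contrast. Report q-values beside the estimates and 95% intervals.
3. State the LEfSe settings and bring its output under the same control.
4. Treat the GvHD Cox models as a separate family with their own q-values. Do not use the LBP result to screen markers out of these models: section 7.3.3.1 expects only some of the GvHD-related genes to come from LBP, so such a screen would discard markers that are in scope.
5. For the 15-versus-15 subset, report a two-group difference (log fold change with a confidence interval), or state that the correlation describes the selected subset and not the trial population.

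This changes SAP wording only and needs no new patients, samples or assays. The price is a shorter list of claimed markers and some lost sensitivity to real but modest associations.

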1.2 Exploratory Aims

- 1.2.1 To determine whether orally-administered *LBP* decreases the incidence of Grade II–IV aGvHD following alternative donor alloHCT.
- 1.2.2 To determine whether *LBP* administration maintains intestinal integrity as measured by mean serum citrulline levels and reduction in mucosal barrier injury (MBI) bacteremia.
- 1.2.3 To measure the effects of *LBP* on the intestinal flora phylogenetic composition during and after alternative donor alloHCT using 16S rRNA gene deep sequencing.
- 1.2.4 To measure effects of *LBP* on intestinal flora function during and after alternative donor alloHCT using metagenomic and metabolite profiling.
- 1.2.5 To measure proposed immunomodulatory effects of *LBP* in mean serum levels of allereactive-induced inflammatory cytokines (IL-2, IL-6, IL-12p70, IFN γ , TNF α , etc.) in patients receiving *LBP* compared to placebo.
- 1.2.6 To determine whether *LBP* administration reduces the incidence of *Clostridium difficile*-associated diarrhea in alternative donor HCT patients.
- 1.2.7 To determine whether *LBP* administration reduces hospital days within the first 120 days post hematopoietic cell transplant (HCT).
- 1.2.8 To define the safety of orally administered *LBP* strains 299 and 299v in alternative donor HCT patients as measured by incidence of *Lactobacillus plantarum* bacteremia.

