4.1 Overview of Treatment Plan

This will be a double-blind, randomized, placebo-controlled, intervention study that will equally allocate 454 children to either *LBP* or placebo for approximately two months. All patients, patient caregivers, direct healthcare providers, pharmacy and the institutional study team will be blinded to the randomization allocation. Sites will receive notification of the study product kit number to dispense to the patient via email at OPEN enrollment submission. The patient should receive the same study product kit number throughout the study. Study participants will receive a course of either *LBP* or placebo for approximately 64 days, starting at the initiation of conditioning regimen and ending at Day 56. However, participants will be followed until Day 120 to ensure capturing development of aGvHD. The table below provides a study overview.

	Start of conditioning	Day 0 (Graft Infusion)	Day 7	Day 14	Day 28 or discharge	Day 56	Day 120
Study Product Administration (LBP or placebo)	●—————●						
Specimen Collection	-Blood -Stool	-Blood -Stool	-Blood -Stool	-Blood -Stool	-Blood -Stool	-Blood -Stool	-Stool

Please see [Section 7.1](#) for specimen requirements.

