- If several doses are missed due to inability to tolerate oral administration (e.g. mucositis or nausea/vomiting), therapy should resume as soon as the patient is able to tolerate oral administration. Please ensure all missed doses are documented in the patient medical record if the patient is in the hospital or patient diary (*available on the COG protocol web page*) if the patient is being treated at home.

Most patients will receive the *LPB* or placebo in both the inpatient and outpatient settings. Adherence to the prescribed regimen will be measured by examination of medication administration records and as documented in the electronic medical record or other hospital source documentation. Patients will be given a diary to document the doses they take at home, which includes instructions for preparation and storage.

Adherence will be defined as administration of at least 80% of the prescribed doses. In the home setting, medication will be dispensed for a specified time period and medication diaries will be completed by families and delivered to the institution on a weekly basis at the time of weekly visits.

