7.1 Required Clinical and Laboratory Evaluations

Studies	Eligibility [§]	First day of conditioning ^{@.&}	Day 0 (Graft Infusion)	Day 7	Day 14	Day 28 or Discharge [%]	Day 56	Day 120
History	X	----	----	----	----	----	----	----
Physical examination, evaluation of GvHD	X	X	X	X	X	X	X	X
Performance status	X	----	----	----	----	----	----	----
Pregnancy test*	X	----	----	----	----	----	----	----
Screening for Clostridium difficile (only if diarrhea at enrollment or first day of conditioning)	X	X ^{&}	----	----	----	----	----	----
Review of LBP administration/patient diary	----	----	X	X	X	X	X	
Blood sample for citrulline and cytokine studies See Section 7.4.1	----	X [^]	X	X	X	X	X ^{a,b}	
Stool sample for correlative studies See Section 7.4.2	----	X [^]	X	X	X	X	X ^b	X ^b

§ All clinical and laboratory studies to determine eligibility must be performed within 7 days prior to enrollment/randomization unless otherwise indicated.

^ Specimen collection on first day of conditioning or anytime within 72 hours before the start of conditioning (prior to chemotherapy). See [Section 7.4.1](#) and [Section 7.4.2](#) for overview of procedures and a Specimen Collection Manual available on the COG protocol web page with further technical detail.

@ The first day of the transplant conditioning regimen is defined as the first day of chemotherapy or TBI, excluding any preceding anti T-lymphocyte antibody therapy. See [Section 4.2.1](#).

% Day 28 or day of discharge, whichever comes first.

* Women of childbearing potential, defined as a female who has had her first menstrual cycle.

& If the patient has diarrhea on the first day of conditioning and repeat stool culture shows *C. diff*, then the patient is ineligible and must be removed from protocol therapy. Reminder: patient condition(s) prior to initiation of protocol therapy must be within parameters required for eligibility. (See [Section 8.1](#))

a Citrulline sample only.

b Blood and stool specimens may be collected within 14 days of the designated time point without being considered a protocol deviation.

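### Exploratory Aim 7 targets hospital days in the first 120 days after transplant, but its formula is one span from admission for conditioning to discharge, which is not total inpatient days; handling of deaths is unspecified.

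*Combined protocol and SAP*

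**What the plan says.** Section 1.2.7 sets the aim as whether LBP "reduces hospital days within the first 120 days post hematopoietic cell transplant (HCT"). Section 9.3, Exploratory Aim 7, repeats that target and then gives the formula: "Total hospital days over the study period is calculated as the duration between the date of admission for conditional therapy and the date of discharge". A parenthesis names the study end date as the alternative end point. I read conditional therapy as conditioning. The comparison follows: "Hospital days will be compared between arms by t-test (or Wilcoxon rank-sum test if assumptions for t-test are not met").

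Three other places bear on the formula.

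- Section 4.1 describes study product "placebo for approximately 64 days, starting at the initiation of conditioning regimen and ending at Day 56".
- Section 4.2.2 expects most patients to take product "in both the inpatient and outpatient settings".
- The visit footnote in Section 7.1 reads "Day 28 or day of discharge, whichever comes first".

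Nothing in the documents says how readmissions count, whether days before Day 0 are subtracted, or how a death enters this outcome.

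**The concern.** The target and the formula differ in both window and content. The target is a count of days in hospital between Day 0 and Day 120. The formula is one interval, opened by one admission and closed by one discharge.

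Patients are expected to go home and keep taking product inside the window, so readmission before Day 120 is possible and should count. If it does not, the analysis cannot see an effect of LBP on readmissions, including those for GI aGvHD that starts after the first discharge. This is the only listed aim that measures hospital use, so a null result could be read as no saving in hospital days when part of the quantity was never counted.

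**Working it through.** The plan gives no sample size, SD or effect size for Aim 7, so there is no figure to reproduce. The check is to apply the formula.

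**Lead-in.** Section 4.1 gives a course of about 64 days ending at Day 56, so conditioning starts about 64 − 56 = 8 days before Day 0. The longest possible span is then about 120 + 8 = 128 days, for a 120-day target. The 8 is approximate: the formula runs from admission, not from the start of conditioning, and Section 4.2.1 excludes preceding antibody therapy from the first conditioning day.

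**Worked patients** (8-day lead-in; discharge and readmission days assumed):

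| Patient | Inpatient days, Day 0–120 | Span to first discharge | Span to last discharge |
|---|---|---|---|
| Home Day 28, no readmission | 28 | 8 + 28 = 36 | 36 |
| Home Day 28, readmitted Day 60 to 90 | 28 + 30 = 58 | 36 | 8 + 90 = 98 |
| Never discharged | 120 | 128 | 128 |

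The first two patients differ by 30 inpatient days. The first-discharge reading shows a difference of 0. The last-discharge reading shows 98 − 36 = 62, because 32 days at home are counted. Neither reading gives the total. For a patient discharged on Day 28, 120 − 28 = 92 days remain in which readmission could occur.

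**Size of what is missed (first-discharge reading).** The difference lost is the between-arm gap in readmission rate times the mean length of readmission.

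- Section 9.4 plans on GI aGvHD of 30% v 18%, a gap of 12 points. If every prevented case would have led to a readmission of 15 to 25 days (assumed), the loss is 0.12 × 15 = 1.8 to 0.12 × 25 = 3.0 days per patient. This is a ceiling for the GI aGvHD route.
- If half of those cases would have led to readmission, it is 0.06 × 15 = 0.9 to 0.06 × 25 = 1.5 days.
- For readmission for any cause, gaps of 5 to 20 points and stays of 10 to 20 days (all assumed) give 0.05 × 10 = 0.5 to 0.20 × 20 = 4 days.

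**Illustrative simulation.** All inputs except the arm size are assumed or approximate: 227 per arm, median first discharge Day 28, lead-in about 8 days, readmission in 50% v 35% with mean stay about 16 days, and 5% deaths in each arm. A true difference of about 2.3 days became about 0.0 under the span to first discharge. Rank-sum rejection at the 5% level was 6%, against 42% when all stays were summed. The 15-point gap is wider than the design effect on GI aGvHD, so this shows the mechanism and does not forecast the trial.

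**Death.** Take a patient who dies undischarged on Day 20. If the span stops at death, the score is 8 + 20 = 28, better than the 36 of a survivor discharged on Day 28. If the study end date means Day 120, the score is 8 + 120 = 128, the worst possible. Summing inpatient days does not settle this: the raw count is 20, below the survivor's 28. A separate rule is needed whichever count is used.

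**The case against.** The strongest defence is that the index stay is a legitimate measure that captures much of what LBP might change. GI aGvHD that starts before discharge can prolong that stay and is counted. So may earlier effects: Section 7.3.1 predicts a shallower fall in citrulline at Day 7 and fewer mucosal-barrier infections. The documents give no split of GI aGvHD onset before and after discharge and no readmission rate. A reader might infer that the formula removes the very days LBP is meant to save; that is too broad, and 1.8 to 3.0 days is only a ceiling.

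The pre-transplant days do not bias the comparison. Under double-blind 1:1 randomisation they balance on average, and a common offset cancels in a difference of means. What remains is the wrong label and some added variation.

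A reader might also infer that an early in-hospital death is scored as a short, good stay, so that the arm with more deaths is favoured. The documents do not establish this. Death is an off-study criterion in Section 8.2, but no sentence ends the Aim 7 span at death. Where Section 9.3 means a patient's own exit it refers to the off-study criteria, whereas Aim 7 uses a different term, and Section 11.9 treats Day 120 as the study's last data point. On that reading the direction reverses. Section 9.3 also expects few early exits. Only the absence of a rule is supported.

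Finally, the aim is one of eight exploratory aims, with no power statement or decision rule. That limits the weight of the point but does not reconcile formula and aim.

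**Conclusion.** The point holds in this form: followed as written, the Aim 7 formula does not measure hospital days in the first 120 days after transplant. That rests on the text alone. Neither meaning of discharge rescues it, and the alternative end point at the study end date closes an open stay without adding later ones.

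The consequences differ in weight. Missed readmissions matter most, at no more than 1.8 to 3.0 days per patient through GI aGvHD, given the planned 12-point effect and assumed stays of 15 to 25 days, and less if some cases start during the index stay. The lead-in of about 8 days is mislabelling and noise. Death handling is unspecified, with no direction of bias established.

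The primary analysis and its conclusion are not touched.

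**What to change.** 1. Define the outcome as inpatient days summed over all admissions from Day 0 to Day 120, and use that definition in both Section 1.2.7 and Section 9.3.
2. Confirm that every admission, readmission and discharge date through Day 120 is collected. The Section 7.2 table has no such row, and the case report forms (Section 12.0) are posted outside these documents, so this cannot be checked here.
3. State what the study end date means, and pre-specify a rule for death before Day 120. One choice is to rank such deaths as worst in the Wilcoxon rank-sum test, which Section 9.3 already names as the fallback. Days alive and out of hospital to Day 120 is another option, but it is a composite and changes the question somewhat; the text does not require it.
4. Keep index length of stay as a descriptive item.

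The cost is a wording change plus, if the dates are not already captured, a small data-entry burden at sites. It should be settled before any unblinded analysis of this aim.

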7.2 Data Collection

The following table represents data that will be collected during the study.

Studies	First day of conditioning [@]	Day 0 (Graft Infusion)	Day 7	Day 14	Day 28 or Discharge [%]	Day 56	Day 120
Review of LBP or placebo administration #	X	X	X	X	X	X	----
Use of TPN/EN (yes or no and days of administration)	X	X	X	X	X	X	X
Use of antimicrobial agents	X	X	X	X	X	X	X
Bloodstream infection	X	X	X	X	X	X	X
Clostridium difficile -associated diarrhea	X	X	X	X	X	X	X

[@]The first day of the transplant conditioning regimen is defined as the first day of chemotherapy or TBI, excluding any preceding anti T-lymphocyte antibody therapy. See [Section 4.2.1](#).

[%] Day 28 or day of discharge, whichever comes first.

[#] Total days product was administered will be collected for each reporting period. See [Section 4.2.2](#).

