9.0 STATISTICAL CONSIDERATIONS

9.1 Sample Size and Study Duration

Based on estimates from Center of International Blood and Marrow Transplant Research (CIBMTR), approximately 1,400 allogeneic SCTs are performed at COG institutions each year with approximately 25% of them (350 per year) meeting the definition of "alternative donor" as defined in this study. If 30% of those eligible are enrolled, the accrual rate will be about 105 per year. Accounting for start-up time and possible delay of up to 4 months between the two stages of the study, we project accrual to the screening stage within 1.2 years and total accrual duration of 5 years. The sample size of 454 (the first 120 for the screening stage and an additional 334 for the confirmatory stage) may be increased to a maximum of 500 patients (up to 132 for screening stage and an additional 368 for the confirmatory stage) to conservatively account for up to 10% loss due to ineligible or not being randomized to a treatment regimen. Evaluable patients are defined as eligible (or meeting repeated eligibility criteria) randomized patients.

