Exploratory Aim 8: This aim will examine the safety of orally administered LBP strains 299 and 299v in alternative donor HCT patients as measured by incidence (yes/no) of *Lactobacillus plantarum* bacteremia. Patients who have at least one incidence (positive) of *Lactobacillus plantarum* during any reporting period is considered evaluable for this aim. We will use the same analytic approach as described for exploratory Aim 6 above.

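### Exploratory Aims 6 and 8 treat only patients with a positive result as evaluable, so neither the C. difficile nor the LBP-bacteremia incidence can be calculated or compared as written

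*Combined protocol and SAP*

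**What the plan says.** Aim 6 in section 9.3 has a yes/no endpoint, occurrence of C. difficile-associated diarrhea. Its analysis set is: "Patients who have at least one incidence (positive) of *C. diff* during any reporting period is considered evaluable for this aim". Its test is: "We will compare proportion of *C. diff* during the study period between arms via the chi-square test".

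Aim 8, also in section 9.3, has a yes/no endpoint of L. plantarum bacteremia and a parallel analysis set: "Patients who have at least one incidence (positive) of *Lactobacillus plantarum* during any reporting period is considered evaluable for this aim". It takes its method from Aim 6.

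Section 9.1 defines the term for the trial as a whole without reference to outcome: "Evaluable patients are defined as eligible (or meeting repeated eligibility criteria) randomized patients". Section 9.2 applies modified intention-to-treat to all evaluable patients. No other sentence gives a denominator for Aims 6 and 8.

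Aim 7 asks whether LBP "reduces hospital days within the first 120 days post hematopoietic cell transplant" (section 1.2.7), but section 9.3 says total hospital days are "calculated as the duration between the date of admission for conditional therapy and the date of discharge (or the study end date").

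**The concern.** A proportion needs the patients without the event in its denominator. Both sentences restrict the set, explicitly for the aim in question, to patients who had the event. They therefore read as aim-specific overrides of section 9.1 and remove everyone who could answer no.

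Aim 8 matters more. It is the only planned between-arm comparison specific to LBP bacteremia, the particular risk of giving a live organism to these patients, and it implements objective 1.2.8. As written it yields no rate in either arm. Other safety oversight is intact: 24-hour reporting of LBP bacteremia (sections 4.2.3 and 11.9), the comparison of mucosal barrier infections (Aim 2), the toxicity data mentioned in section 9.2, and DSMC review (section 12.2). Case reports alone do not provide a planned rate per arm with its uncertainty.

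Aim 7 is a separate, lesser mismatch. Its span starts before transplant although the objective counts days after it, and one admission-to-discharge interval cannot represent a patient who is readmitted.

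**Working it through.** The plan states no rate, power or significance level for Aims 6 and 8, so there is no figure to reproduce. The check applies the rules as written.

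**1. Literal rule.** Let a and b be the numbers of cases in the two arms. The evaluable set is those a + b patients, so the table of arm by yes/no is:

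| | Yes | No |
|---|---|---|
| LBP | a | 0 |
| Placebo | b | 0 |

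The expected count in each No cell is (row total × 0)/(a + b) = 0. Pearson's statistic divides by expected counts, so it is undefined whatever a and b are.

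- 5 v 3 cases: 5/5 v 3/3, 100% in both arms, no test.
- 5 v 0 cases: 5/5 v 0/0, no test.
- 0 v 0 cases: empty set, no rate.

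Software confirms this. The chi-square routine stops on a zero expected frequency for the first two tables, and Fisher's test on tables of this form gives p = 1.0 with an undefined odds ratio.

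**2. With a proper denominator.** Arm sizes from section 9.4 are 227 (confirmatory) or 60 (if the trial ends after screening). For zero events the exact two-sided 95% upper limit is 1 − 0.025^(1/n):

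- n = 227: 1.6%
- n = 60: 6.0%

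For 5/227 (2.2%) the exact 95% interval is 0.7% to 5.1%.

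**3. Choice of test for a rare event.** With equal arms, the expected number of events per arm is half the total, so fewer than 10 events in all leaves expected counts below 5. With x events against 0 and N patients in total, uncorrected chi-square reduces to N·x/(N − x). For 5 v 0 with N = 454 that is 454 × 5/449 = 5.06. The documents give no expected bacteremia rate, so these splits, at 227 per arm, are illustrations:

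| Split | Chi-square, uncorrected | Chi-square, continuity-corrected | Fisher |
|---|---|---|---|
| 4 v 0 | p = 0.045 | p = 0.132 | p = 0.123 |
| 5 v 0 | p = 0.025 | p = 0.072 | p = 0.061 |
| 6 v 0 | p = 0.014 | p = 0.040 | p = 0.030 |

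The plan does not say whether the chi-square is corrected.

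**4. Aim 7.** Section 4.1 describes dosing for "approximately 64 days, starting at the initiation of conditioning regimen and ending at Day 56". If admission coincides with the start of conditioning, about 64 − 56 = 8 pre-transplant days per patient enter the total. Take an assumed patient discharged on Day 28 and readmitted from Day 60 to Day 70:

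- inpatient days after transplant: 28 + 10 = 38
- formula, first discharge: 8 + 28 = 36 (the 10 readmission days are lost)
- formula, last discharge: 8 + 70 = 78 (32 days at home are counted)

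The text does not say which discharge is meant.

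**The case against.** The best reply is that the intent is plain. Both endpoints are labeled yes/no, Aim 6 compares a proportion, section 9.1 supplies a denominator, and section 9.3 uses C. difficile incidence as a covariate in models of the trial population, so the variable must exist for patients without it. Section 11.9 continues data collection on all patients through Day 120. An analyst would be unlikely to produce 5/5 v 3/3, and rates stay obtainable from case counts and arm sizes.

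That is a fair account of what was probably meant, but it does not repair the rule. The sentences are specific to their aims, and setting them aside still leaves the denominator open: all eligible randomized patients (section 9.1), those with at least one dose (the screening comparison in section 9.3), or a set without patients who never received conditioning (section 9.2, for the primary outcome).

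Other parts of the reply stand:

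- The gap between chi-square and Fisher largely disappears with a continuity correction, so the test is a secondary matter.
- The small-count problem is unlikely to affect Aim 6. At the pilot's 20% rate, 227 patients would give about 45 events per arm.
- Pre-transplant days in Aim 7 fall in both randomized arms, so they mainly add noise. The figure of 8 is approximate, since section 4.1 says about 64 days.

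**Conclusion.** The concern holds. As written, Aims 6 and 8 produce no incidence and no test for any pattern of results, and they contradict section 9.1. This follows from the definitions alone and needs no assumption about event rates. The p-values in step 3 and the Aim 7 example do rest on assumed counts and dates; the 8-day figure assumes admission on the first day of conditioning.

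The likely cause is an event definition written as an evaluability rule. The consequence is limited: the aims are exploratory, and the primary analysis, screening decision and sample size do not change. It should still be corrected before unblinding, because Aim 8 is the planned comparison of the product's specific risk and its denominator is otherwise left to be chosen afterwards. The Aim 7 formula does not measure its stated objective and should be corrected at the same time.

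**What to change.** **Aims 6 and 8.** Replace each evaluability sentence with an event definition: at least one positive result in any reporting period through Day 120 counts as yes, anything else as no. Then name the denominator. For Aim 6, use the evaluable patients of section 9.1. For Aim 8, all randomized patients who received at least one dose is a usual safety set; using the section 9.1 set would also remove the contradiction, provided the choice is written down. Report incidence per arm with exact 95% confidence intervals, and use Fisher's exact test for bacteremia.

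**Aim 7.** Define the outcome as the sum of inpatient days from Day 0 to Day 120, including readmissions, and state how patients who die before Day 120 are handled.

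**Cost.** Aims 6 and 8 need wording only, because section 7.2 already collects bloodstream infection and C. difficile diarrhea in every reporting period. Aim 7 needs wording plus a check that the case report forms record every admission and discharge date. The section 7.2 table lists none, but it also omits GvHD, so it is not a complete list of what is collected.
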